### SECTION 1. General Information

1. Level of Review:  Expedited (Complete Addendum 1 and submit with the application)  
*Expedited Research must meet this definition: The probability and magnitude of harm or discomfort anticipated in the research are not greater in and of themselves from those ordinarily encountered in daily life or during the performance of routine physical or psychological examination or tests. 45 CFR 46.102(i).*
- Full Board  
*Full Board Research meets this definition: The probability and magnitude of harm or discomfort anticipated in the research are greater in and of themselves from those ordinarily encountered in daily life or during the performance of routine physical or psychological examination or tests, or are not in a category allowed for Expedited Research – 45 CFR 46.110.*

### The application will not be processed until the PI, Co-PI, and Key Personnel have completed CITI training.

- The PI, Co-PI and Key Personnel must have completed the appropriate CITI training within the last 5 years.
- **Biomedical Health Sciences Researchers** must complete CITI – Good Clinical Practice and CITI - Biomedical Research.
- **Social Behavioral Researchers** must complete CITI – Social/Behavioral Research.
- For Non-WSU Personnel, provide equivalent certificates or contact the IRB to access WSU CITI training. For non-English speaking personnel, contact the IRB at [[contact]](mailto:[contact]).
- For CITI training options, visit the CITI website at <http://www.citiprogram.org>
- If you have any further questions, contact the IRB Program Assistant at [name] or see the webpage <http://www.irb.wsu.edu/CITI.asp> or email [[contact]](mailto:[contact]).

2. Human Participant Training Record (CITI –WSU) of Principal Investigator:  
Date of Training: **9/26/15** Ref #: **4503372**

3. Estimated Study Start Date: 6/20/20

4.  Yes  No Is this research supported in whole or in part by a grant or contract?  
If yes, complete below:

Funding Agency(s), Foundation, or Business: Institute of Translational Health Sciences and Rayce  
Rudeen Foundation

PI on Grant/Contract: [name] ORSO #:

Grant Title/Contract: Academic/Community Partnership Award.

Check if funding is from: National Institute of Health:

If required, has registration been completed with clinicaltrials.gov?  Yes  No  
(Include Addendum 8.)

Provide either the registration number, or a reason this has not been completed: not required

5.  Yes  No Does the research require another IRB's review? If yes, complete below.

Name of the IRB:  FWA number or equivalent number:

NOTE: PI is responsible for securing approval and keeping a copy of the documentation.

6.  Yes  No Does the PI, Co-PI, or any other person responsible for the design, conduct, or reporting of this research have an economic interest in or act as an officer or director of any outside entity whose financial interest would reasonably appear to be affected by the results of the study? If yes, complete below:

Name of the person with potential financial conflict of interest (FCOI):

Explain the FCOI:

Explain how the potential FCOI will be managed below. (If the economic interest is a "significant economic interest" as defined in WSU's Executive Policy #27, submit the management plan established with the Conflict of Interest Committee.)

7.  Yes  No Has any PI, Co-PI, or any other person responsible for the design, conduct, or reporting of the research received or will receive any financial assistance (other than a WSU grant or WSU award) including, but not limited to: equipment, staff, data transfers, proprietary information, or financial help? If yes, complete below:

Name of the recipient(s):

Explain the assistance:

 See also: <https://research.wsu.edu/resources-researchers/operations-support/coi/>

Explain how the potential conflict of interest will be managed below. (If the economic interest is a "significant economic interest" as defined in WSU's Executive Policy #27, submit the management plan established with the Conflict of Interest Committee.)

8.  Yes  No Is the proposed research study conducted at an outside (non-WSU) facility or entity (such as a hospital, clinic, school, school district, factory, office, etc..,)?

If yes, provide the name(s) of the facility or entity: none

*The researcher has an obligation to ensure that the outside entity is aware of the proposed research study and has no objections (i.e. agrees to participate). In order to respect the rights of entities, research to be conducted at these locations may require a letter from an authorized representative to the WSU IRB or researcher acknowledging the research study and their willingness to allow the proposed research.*

9. Provide the location(s) or address(es) at which research will be conducted:

10.

11.  Yes  No Is the proposed research study specifically targeting Alaska Natives/Native Americans as a subject population?

*In order to respect the sovereign governments, research to be conducted on Native American tribal lands will require a letter from the Tribal Council (or equivalent authorized signatory) to the WSU IRB acknowledging the research study and their willingness to allow the proposed research.*

12.  Yes  No Does the research require approval from other WSU compliance committees?  
*Radiation Safety Committee (RSC), Institutional Animal Care and Use Committee (IACUC), or Institutional Biosafety Committee (IBC).*

If yes, PI has responsibility to seek approval from the other committees required for this research. Work cannot start until final approval is received from all appropriate committees.

## SECTION 2. Study Description

Provide a brief summary of the proposed research. Use lay language and avoid technical terms. IRB members not familiar with the area of research must understand the nature of the research. The application will be returned without further review if summary is too technical.

1. Brief (500 words or less) summary of research study:

Purpose:

The purpose of the COMFORT pilot study is to examine the feasibility, effectiveness, and acceptability of a project that aims to removes barriers to receiving chronic non-cancer pain treatment by increasing the usage of non-pharmacological pain management therapies in the

 See also: <https://research.wsu.edu/resources-researchers/operations-support/coi/>

Spokane, WA area. Innovations in the field of chronic non-cancer pain management are needed to ensure that compassionate conversations occur when opioid dose tapering is being considered and that adults being managed in primary care settings have access to safe and effective pain management options. The research team aims to collect evidence about the receptivity and effects of non-drug interventions that are known to be helpful for pain when offered to patients with pain who are considering or attempting tapering of opioid dosages. With U.S. opioid overdose deaths on the rise, more patients with chronic non-cancer pain are being asked to reduce their opioid use while insurance plans do not cover many non-drug therapies that have shown to be effective. This project will build evidence about how free access to non-drug options may be received by patients and whether this approach can aid in reducing reliance on opioids for pain management. We will provide all options and study activities using telephone or internet to protect against contagious disease during the COVID-19 pandemic. We will also investigate participants' satisfaction and receptivity to online options in times of pandemic.

Design:

The COMFORT project will utilize a non-randomized one group pre-postest design to investigate feasibility, acceptability, and preliminary effects of a pilot program to invite chronic non-cancer pain patients by their primary care providers to accept free consultations and short-term treatment with diverse healthcare practitioners (e.g. chiropractors, physical and massage therapists, and yoga therapists). Invitations will be extended by healthcare providers to patients who from an urban health clinic that serves low income adults and who have an opioid dose reduction under consideration. Measures of pain, mood, quality of life will be examined for preliminary effects as well as measures of the pilot project feasibility (percent participants approached and recruited, percent consented) and acceptability measures (satisfaction, percent of sessions attended). Measurements will be taken before and after 30 participants are invited to try one of four non-drug pain management options at no charge. All therapies and study activities will be delivered using zoom technology for telehealth and/or phone to protect patients and research staff during times of pandemic.

Procedures: (Using lay language, provide a complete description of the study procedures, including the sequence, intervention or manipulation (if any), drug dosing information (if any), use of records, and subject time required. For projects involving receipt of data or "big data", include a list of fields and/or overlapping source layers (i.e., combining newspaper accident reports, police reports, and medical charts) that will be received; also include a process for who will strip unnecessary data and how this will be completed. For projects involving multiple phases or complex designs, attach flow chart(s) describing the sequence of study procedures.)

Project investigators will begin by working with community-based primary care providers to develop a process to identify and invite adults diagnosed with chronic non-cancer pain and prescribed opioids to try a non-opioid treatment option plan using the COMFORT project's recruitment script (Appendix). Interested participants will receive study information and be contacted via telephone by study staff and screened for eligibility; those individuals deemed

eligible will be invited to an informed consent meeting. Post-consent a baseline survey will be sent electronically and once completed, a pain assessment will be conducted by a registered nurse (the PI, a certified pain management RN) via telehealth. Each participant will be asked to choose two treatment modalities for a consultation and brief trial and schedule a weekly 45-minute appointment for six weeks; individuals will receive three rounds of the two different modalities they choose using a shared-decision making process that allows guidance by research staff who are knowledgeable about the therapy selection. Data will be collected in multiple ways including via healthcare practitioners (e.g. McCaffery Initial Pain Assessment Tool, Functional Rating Index, etc.), participants (e.g. surveys for demographic information, health history, pain level, satisfaction, and medication usage), study staff (e.g. attendance records) and from clinical records (medication dose prescribed) using IRB-approved protocols. An exit interview will be audio-taped to capture more specific information about patient experiences. See Data Collection Plan table below. Data will be analyzed using descriptive summary statistics, paired t tests for pre and post-test effect size calculations, and content analysis for qualitative data. Sample size of 30 was chosen based on the number needed to generate sufficient pilot data to calculate effect sizes for future trials (Jacobsen & Melnyk, 2012).

All study activities including the informed consent meeting will be completed using telehealth principles using Zoom technology and/or telephone. Participant will review consent document and be informed that consent is implied by completion of the initial baseline survey. No signatures will be collected but the participant will receive a mailed or emailed copy of the consent. We will use WSU-licensed Zoom accounts.

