### **Data collection plan**

Measure	T1	T2	T3
	Week 0	Week 3	Week 6
Baseline Measures			
Demographics & Medical History	✓		
Modality Selection Questionnaire	✓		
McCaffery Pain Assessment (by RN)	✓		✓
Functional Index (by RN)	✓		
Medication goal	✓	✓	✓
Primary Self-reported Outcomes			
Pain Intensity and Pain Interference (PROMIS)	✓	✓	✓
Self-efficacy of Symptoms/Emotions (PROMIS)	✓	✓	✓
Current Opioid Misuse Measure (COMM)	✓	✓	✓
Depressive Symptoms (PHQ-8)	✓	✓	✓
Anxiety (GAD)	✓	✓	✓
Spiritual Well-being Scale	✓		✓
Interpersonal Needs Questionnaire	✓	✓	✓
Additional Data			
Program Satisfaction Questionnaire		✓	✓
Post Program Interview			✓
Program Engagement (program attendance records)	✓	✓	✓
Medication Dose (clinical record)	✓		✓

Data collection will be taken at baseline, Week 3 and Week 6.

**Cultural Competency: (For projects involving select populations, provide the researchers' qualifications for working with the subjects.)**

The PI has conducted 10 studies on chronic pain populations and has received specialized training and certification in pain management nursing.

2. What will each participant be asked to do in their role as a participant?

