Interested participants will agree to be screened for project eligibility via telephone after receiving study information; if deemed eligible, participants will be asked to attend an informed consent meeting with study staff held over phone or Zoom videoconferencing that will last about 1 hour. After consent a registered nurse will conduct a thorough pain assessment on each participant guided by the McCaffery Initial Pain Assessment Tool and the Functional Rating Index (20 min). The participants will be asked to choose one non-opioid treatment modality (selecting from yoga, physical therapy, massage or chiropractic therapy). After selection of the treatments, participants will be asked to schedule and attend six treatment appointments (three sessions of 2 different modalities) over the course of six weeks. Prior to the first assessment by the nurse, participants will be asked to complete a baseline survey via Qualtrics electronic survey that includes baseline demographic and health history information as well as create one goal related to their prescribed opioid use (e.g. reduce their dose or avoid a dose increase). Participants must be willing to attend treatment sessions that last for 45 minutes weekly and take place primarily using Zoom videoconferencing and phone back-up. Attendance at each scheduled appointment will be logged and participants will be asked to complete surveys after

each modality trial focused on satisfaction, pain level, symptoms, and medication usage (see Appendix for survey items). At the end of the six week study period an exit interview via phone of 60 minutes or less will be conducted with each participant which will include questions related to identifying their preferences and the challenges they experienced with each treatment modality, goal setting/achievement, and the COMFORT process as well as their desire and likelihood of continuing each treatment option they trialed during the project. Because we are using telehealth, all “treatments” will be guided by the practitioner, representing a consultation and educational experience versus a “hands-on” treatment approach that would normally be used in person. Eg. Chiropractor may assist in teaching posture awareness by watching the person walk and giving advice, and massage therapist may have participants use tennis balls to roll on painful areas to simulate massage – these are activities within the practitioners’ usual scope and range of patient educational activities.

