### SECTION 3. Data Collection Methods

Check all method(s) to be used. If participants will be shown media (such as a video), provide a copy of the media, or a link to its location, or a thorough description of the material contents to the IRB.

1.  Survey/Questionnaire       Phone       In person       Internet       E-mail       Postal mail

If checked, submit copies (if applicable, translated versions) of all the data collection methods and questions mentioned under survey/questionnaire. Use a secure system for digital methods, such as Qualtrics, which is WSU approved.

2.  Interview       One-on-one       Focus group       Oral history       Other:

If checked, submit copies (if applicable, translated versions) of all the data collection methods and questions mentioned under Interview.

3.  Observation of Public Behavior       Classroom       Public meetings       Other:

4.  Examination of Archived Data/Secondary or Records that contain any of the direct or indirect identifiers listed under HIPAA or FERPA.

See also: <https://policies.wsu.edu/prf/documents/2017/04/90-78-use-ssn-forms.pdf/>

Briefly describe who will provide the record and what it will contain:  Clinic partners will provide a record of medication dose ordered at baseline and at 6 weeks

List all fields that the researchers will receive:  name (needed for communication of data) and  medication dose, date prescribed, any additional information in chart records regarding medication dose changes

DO NOT DELETE OR ALTER ANY PART OF THE APPLICATION

If data is being de-identified state who will do this and when: de-identification will occur by PI after receiving the information from the clinic by creating a spreadsheet with de-identified codes

If the research has a Memorandum of Understanding (MOU) or Data Sharing Agreement (DSA) with the entity providing the data or records, a copy of this Memorandum or Agreement must be provided to the IRB.

5.  Taste Evaluation  
 Wine/alcohol  Non-wholesome food  
*(Wholesome foods can be reviewed under Exemption Determination.)*
6.  Examination of Human Pathological or Diagnostic Tissue Specimens (e.g. blood, bodily fluids...)
7.  Experimental (Unproven or Untested Procedures)  
 Biomedical  Psychological  Other:
8.  Recordings  
 Voice  Video  Digital  Image  Other

If Other is checked (e.g., GPS or accelerometer recordings), describe:  

Check the purpose of the recordings:  For transcription  Other

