Psychological/ emotional discomfort/distress:

Participants will be told on informed consent about potential psychological risk with these statements: "It is possible you will feel stress or psychological discomfort when you are answering personal questions or engaging in any of the non-drug treatment options. You are encouraged to contact any member of the study team if you feel you need additional counseling or other support, and we will refer you to the appropriate services."

Physical harm/discomfort/:

Occasionally, participants may have adverse effects from any one of the chosen non-drug treatment options such as pain, muscle strain, or increased fatigue. These risks will be reduced through the screening histories, physical exam by each treatment provider, and your own communications with providers about your body and preferences. You will not be forced to do anything you are not comfortable doing or believe may cause you harm.

We have chosen experienced providers to provide treatments who have many years of evaluating patients and who will take every precaution to preserve your safety and well-being.

Significant time: Recognizing that this study entails significant time, we will provide each participant with a written schedule and be sure they understand the time commitment prior to consenting. We will allow flexibility in certain aspects of the study when feasible, such as the appointment days and times and provide reminder calls..

5. In the event that any of these potential risks occur, how will it be handled (e.g. compensation, counseling, etc.)? Include supporting materials.

Explain in detail:

Privacy/confidentiality: Known breaches of confidentiality will be reported to participants and researchers will make every attempt to assure future data protections. Conversations will occur in private areas as much as possible. Medical and eligibility screenings will take place in private.

Psychological/ emotional discomfort/distress: As informed in the consent process, if the study staff learns that depression screening or other study data suggests the possibility of severe or

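### Effect sizes come only from a pre/post paired t test, so people lost after Week 3 drop out of the estimate although their Week 3 scores could correct much of the bias

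*Combined protocol and SAP*

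**What the plan says.** The quantitative plan is one sentence in Section 2 (Procedures), which names descriptive statistics, "paired t tests for pre and post-test effect size calculations", and content analysis of the qualitative data. The sample size rests on the same quantity: "Sample size of 30 was chosen based on the number needed to generate sufficient pilot data to calculate effect sizes for future trials". The Design paragraph describes a "non-randomized one group pre-postest design".

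The Data collection plan states "Data collection will be taken at baseline, Week 3 and Week 6". Its table has seven rows of primary self-reported outcomes. Six are ticked at all three times: PROMIS pain, PROMIS self-efficacy, COMM, PHQ-8, GAD and Interpersonal Needs. Spiritual Well-being is ticked at Weeks 0 and 6 only. Section 2, item 2 also places surveys after "each modality trial focused on satisfaction, pain level, symptoms, and medication usage".

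Opioid dose has a separate source (Section 3, item 4): "Clinic partners will provide a record of medication dose ordered at baseline and at 6 weeks". On retention, Section 8, item 4 allows flexibility in aspects "such as the appointment days and times and provide reminder calls". Nowhere do the documents give an expected dropout rate, an analysis population or a rule for a missing survey.

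**The concern.** A paired t test needs both scores. With post-test read as Week 6 and no imputation rule, a participant who answers at Weeks 0 and 3 and is then lost adds nothing to the effect size. Descriptive statistics may display that Week 3 score but do not correct the estimate.

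This matters if loss is selective. With one group, no comparison arm can offset it. If people who worsen are less likely to return the last survey, completers look better than the enrolled group, and that inflated figure is what the plan hands to future trials. The confidence interval shows sampling error but not this bias.

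The concern is limited to the survey outcomes, because clinic-record dose need not be lost when a survey is.

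**Working it through.** **Inputs from the documents.** n = 30; one group; Weeks 0, 3 and 6 for six of seven primary rows; paired t test as the only effect-size method. The figure of 30 has no stated alpha, power, SD or dropout rate, so there is no calculation to reproduce.

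**Assumptions, because the documents give none.** Scores T1, T2, T3 (Weeks 0, 3, 6) are normal with SD 1, higher is worse, and there is no true change. Correlations are compound-symmetric (CS) 0.5 or 0.7, or autoregressive (AR) with lag-one 0.5 or 0.7, so the Week 0-6 correlation is 0.25 or 0.49 under AR. The log-odds of missing Week 6 rise by 0.5, 1 or 2 per baseline SD of Week 0-3 worsening (odds ratios 1.6, 2.7, 7.4). Loss is 10, 20 or 30%.

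**Step 1: completers' bias.** If loss depends on T2-T1 only,

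E(T3-T1 | stay) = b × E(T2-T1 | stay), with b = (1 - r12 - r13 + r23) / (2 - 2·r12).

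This gives b = 0.5 for CS, (1 + 0.5)/2 = 0.75 for AR 0.5, and (1 + 0.7)/2 = 0.85 for AR 0.7.

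Worked case: CS 0.5, slope 1, 20% loss. The intercept that gives 20% loss is -1.65. By quadrature, the mean Week 3 change is +0.693 in those lost and -0.173 in those who stay (check: 0.2 × 0.693 = 0.8 × 0.173 = 0.139). The completers' mean Week 6 change is therefore 0.5 × (-0.173) = -0.087, a false improvement of 0.087 SD.

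False improvement in all settings at 20% and 30% loss:

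| Loss | Slope | CS 0.5 | CS 0.7 | AR 0.5 | AR 0.7 |
|---|---|---|---|---|---|
| 20% | 0.5 | 0.048 | 0.029 | 0.072 | 0.050 |
| 20% | 1 | 0.087 | 0.055 | 0.130 | 0.093 |
| 20% | 2 | 0.131 | 0.089 | 0.196 | 0.152 |
| 30% | 0.5 | 0.071 | 0.044 | 0.107 | 0.074 |
| 30% | 1 | 0.126 | 0.081 | 0.190 | 0.137 |
| 30% | 2 | 0.187 | 0.129 | 0.281 | 0.219 |

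At 10% loss the ranges for the three slopes are 0.02-0.04, 0.03-0.07 and 0.05-0.11.

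**Step 2: scale.** The standard error of the mean change with 30 pairs is sqrt(2(1 - r)/30): 0.141 at r = 0.7, 0.183 at 0.5 and 0.224 at 0.25. At 20-30% loss the nominal 5% paired test rejects 5-7%, 6-11% and 8-18% of the time at the three slopes.

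**Step 3: using Week 3.** A repeated-measures mixed model (REML, unstructured covariance, Kenward-Roger) was simulated with n = 30 at 20-30% loss, 4,000 studies per setting.

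| Loss mechanism | Completers | Mixed model |
|---|---|---|
| (a) Observed Week 3 worsening | bias as tabled | bias at most 0.007; rejects 4.8-6.9%; SE 5% smaller to 10% larger |
| (b) As (a), half of dropouts also miss Week 3 | biased | 19-34% of the bias remains (slopes 1-2) |
| (c) As (a), all dropouts miss Week 3 | biased | 48-73% remains |
| (d) Unseen Week 6 change | bias 0.06-0.50 | 50-76% remains |
| (e) Random | unbiased | unbiased; SE 2-8% smaller |

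**Step 4: what a future trial would inherit.** A separate simulation (20,000 runs per setting) took a true improvement of 0.30 SD, 20% loss, odds ratio 3 per SD of Week 0-3 change, and equal correlations of 0.5 or 0.7. Completers gave 0.37-0.39; maximum likelihood with Week 3 gave 0.30. At equal SD, a trial sized on 0.38 would enrol (0.30/0.38)² = 62% of the patients needed.

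**The case against.** Five points can be made for the plan.

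- **Post-test is not defined.** Section 2 never says it is Week 6, and the plural leaves room for a Week 0-3 test as well. This is a fair limit on wording. But an added Week 0-3 test would still leave the Week 0-6 effect size to those with both surveys.
- **The harm is conditional.** It needs material loss, loss that follows worsening, and Week 3 scores in those lost. Nothing in the documents makes case (a) likelier than (c) or (d), and someone who stops before Week 3 may miss both surveys. This stands and is why confidence is medium. Reminder calls, flexible scheduling and the Week 6 exit interview may also limit loss.
- **Mild selection is small beside the noise.** At slope 0.5 and a Week 0-6 correlation of about 0.5-0.7, the bias is 0.03-0.07 SD against a standard error of 0.14-0.18, and the two methods' rejection rates are much alike. This also stands.
- **The larger threat is elsewhere.** Without a control, and with recruitment at pain of at least 5 out of 10 (Section 6, item 2), regression to the mean affects the estimate even with complete data. That is true, and no missing-data method repairs it, but it is no reason to add a second, avoidable bias.
- **The remedy is technical for a lay form.** Section 2 asks for lay language, and dividing by the baseline SD is a separate choice. The first is a matter of where the text goes; the second does not affect the case for the model.

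**Conclusion.** The concern holds, as a change that should be made rather than one that invalidates the pilot. The plan's sole effect-size method discards Week 3 scores already scheduled for six of seven primary rows, and nothing says how missing surveys are handled. If 20-30% are lost and loss follows observed Week 3 worsening, completers show a false improvement of 0.03-0.28 baseline SD; with a Week 0-6 correlation of about 0.5-0.7 the upper end is 0.22. The model removes nearly all of that, part of it when dropouts also miss Week 3 or loss follows unseen Week 6 change, and has nothing to remove under random loss. Dropout rate, mechanism and correlations are all assumed, so confidence in the size is medium. That the plan leaves these scores out of the Week 0-6 effect size rests only on reading post-test as Week 6.

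**What to change.** Replace the paired t-test phrase in Section 2 (Procedures) before outcomes are examined. A plain sentence can stand there, with the detail attached:

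1. For outcomes measured at Weeks 0, 3 and 6, fit a repeated-measures linear mixed model (REML, categorical time, unstructured covariance, Kenward-Roger degrees of freedom) using every participant with any score. The Week 6 minus Week 0 contrast with its 95% CI is the principal result; the effect size divides it by the baseline SD of all enrolled.
2. Keep the paired analysis for Spiritual Well-being and clinic-record dose, which have Weeks 0 and 6 only.
3. For every outcome report the number of pairs, the SD of change and the pre-post correlation.
4. Add one sensitivity analysis that shifts dropouts' predicted Week 6 values by 0 to 1.5 baseline SD in the worse direction. The largest shift needed to offset what the model leaves in cases (c) and (d) is 1.03 SD. The full range moves the mean change by up to 1.5 × 0.20 = 0.30 SD at 20% loss and 1.5 × 0.30 = 0.45 SD at 30%.

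**Cost.** A few sentences and slightly more analysis; no added patients, visits or instruments. With complete data the contrast, standard error and degrees of freedom equal those of the paired t test (checked at n = 30). In case (a) there are two downsides: the standard error can be up to 10% larger than the completers', and the model-based standard error can be up to 10% too small (rejection up to 6.9%). In cases (b) to (d) the correction is only partial.

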**Check all that apply. Submit a copy of all the materials that will be used.**

Person to person solicitation

Snowball sampling

Phone

Postal mail

E-mail

Poster

Media (TV, newspaper, radio, web site, social media) Specify:

IRB Approved Listserv:

Subject Pool or Recruitment Pool:

Other:

None (e.g., for studies using existing specimens or secondary data)

2. How will potential subjects be identified? How will potential subjects be approached? Answer for each subject group.

Explain in detail: We will recruit up to 30 participants from the CHAS clinics in the Spokane region who are prescribed any opioid for any chronic, non-cancer-based painful medical condition (greater than 3 months) and report at least moderate (5) pain symptoms on the Numeric 0-10 Pain Scale.

Clinic staff will provide potential participants a study flyer either in person if they are in clinic or electronically if seen in telehealth visit and ask if they would like to be contacted with further information (Appendix 1). Potential participants will have the option of contacting research team members directly using a private voice mail. A standardized script will be used to guide the invitation and limit coercion that states: (Appendix 1). If potential participants agree, they will receive a copy of the informed consent and will be asked if they wish to be screened for eligibility. Research assistants who have received training in screening will proceed with the screening process. If determined to be eligible and they agree, participants will be contacted by a member of the research team for the informed consent process. Their preferred contact information will be collected on a HIPAA-compliant form that will remain secure at their facility's office until the information is relayed to the researchers by phone or in person. Potential participants may choose to contact researchers on their own using the contact information on the informed consent.

Flyers will be made available for distribution to the clinic staff for internal communications or to be posted in public view at the discretion of each facility's administration team (Appendix).

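### Does justifying N=30 only by effect sizes from an uncontrolled pre-post change require a change to the plan?

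*Combined protocol and SAP*

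**What the plan says.** Section 2 (Study Description) sets out the design, the analysis and the sample size.

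- **Design.** "The COMFORT project will utilize a non-randomized one group pre-postest design to investigate feasibility, acceptability, and preliminary effects". There is no comparison group.
- **Analysis.** Descriptive statistics, content analysis of the interviews, and "paired t tests for pre and post-test effect size calculations".
- **Sample size.** "Sample size of 30 was chosen based on the number needed to generate sufficient pilot data to calculate effect sizes for future trials", supported by a citation. No alpha, power, assumed effect, SD, target interval width or allowance for loss is given.
- **Other measures.** The Design text also names "measures of the pilot project feasibility (percent participants approached and recruited, percent consented) and acceptability measures (satisfaction, percent of sessions attended"). These are not tied to the number 30.
- **Purpose.** The study is called a pilot, and its aim is to "examine the feasibility, effectiveness, and acceptability of a project". The options are studied "when offered to patients with pain who are considering or attempting tapering of opioid dosages".

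On enrolment, Section 6 item 2 says "We will recruit up to 30 participants from the CHAS clinics in the Spokane region". Section 5 item 1 calls 30 approximate and lets actual enrolment vary by 10% either way without an amendment, which is 27 to 33.

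**The concern.** Three features together make the rationale look unsound.

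1. **No control.** A pre-post change mixes any programme effect with natural course, expectation and concurrent changes in care. An opioid taper may be under way in the same weeks, so even the direction of the bias is uncertain. For pain, the recruitment text asks that patients "report at least moderate (5) pain symptoms on the Numeric 0-10 Pain Scale". If that threshold is applied at entry, some regression to the mean would be added. It is absent from the numbered eligibility list in the same section, so its effect cannot be sized.
2. **Low precision.** About 30 pairs give a wide interval for a standardized change, and losses would widen it.
3. **No limit on use.** The only stated purpose of N is to inform future trials, and effectiveness appears among the aims. A later team could take the paired value as the expected difference between arms.

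At stake would be a later controlled trial of the wrong size. The plan also passes over the feasibility and acceptability measures, which a single group can estimate without a control arm.

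**Working it through.** **Can N=30 be reproduced?** No. The plan gives no inputs from which to derive it. Assuming a two-sided 5% level, a paired t test with 30 pairs has 75% power at a standardized change of 0.5, and 80% power at about 0.53. These figures neither confirm nor contradict 30.

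**Precision of the paired effect size.** Let d_z be the mean change divided by the SD of change, so that t = d_z√n. The 95% limits are the noncentrality values that put the observed t at the 2.5% and 97.5% points of the noncentral t distribution on n − 1 degrees of freedom, divided by √n. The observed values are assumptions. For n = 30 and d_z = 0.5, t = 0.5 × √30 = 2.74.

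| Pairs | Basis | Observed d_z | 95% CI |
|---|---|---|---|
| 33 | 10% above 30 | 0.5 | 0.13 to 0.86 |
| 30 | planned | 0.5 | 0.12 to 0.88 |
| 27 | 10% below 30 | 0.5 | 0.10 to 0.90 |
| 24 | assumed 20% loss | 0.5 | 0.07 to 0.92 |
| 30 | planned | 0.3 | −0.07 to 0.66 |

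For the mean change itself, the half-width is t(0.975, n − 1)/√n. That is 2.045/√30 = 0.37 SD of change with 30 pairs, and 2.069/√24 = 0.42 with 24.

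**What a misreading would cost.** Suppose a later two-arm trial compares change scores and takes d_z = 0.5 as the between-group effect (two-sample t test, two-sided 5%, 80% power). It needs 64 per arm. The limits 0.876 and 0.116 would give 22 and about 1,170 per arm. If a control arm would show a share s of the change, the true effect is 0.5 × (1 − s). The shares are assumptions.

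| Background change | True effect | Power at 64 per arm |
|---|---|---|
| none | 0.50 | 80% |
| 25% of the change | 0.375 | 56% |
| 33% | 0.333 | 46% |
| 50% | 0.25 | 29% |
| worsening of 0.1 SD | 0.60 | 92% |
| worsening of 0.2 SD | 0.70 | 98% |

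The arithmetic is sound, but every row except the first needs a use that the plan does not state and a control-arm change that it does not give.

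**Would resting N on feasibility be better?** An illustration is 24 of 30, with exact 95% limits of 61% to 92%. None of the listed measures is clearly a count out of 30:

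- Percent recruited and percent consented are taken over patients approached, a number that the plan does not fix.
- Percent of sessions attended is taken over scheduled sessions, up to 30 × 6 = 180, clustered within participants. An exact binomial interval fits neither those sessions nor a mean of participant percentages.
- Satisfaction comes from a questionnaire, so it is not evidently a proportion.

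That rationale would need a new measure, such as a completion threshold. Writing it in without one would introduce an error.

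**The case for a change.** The strongest case for a change is that calling the effects preliminary labels them without restricting their use. N has a single stated purpose, and that purpose points to future trials. Effectiveness is listed as an aim, and Section 8 item 7B expects the study to inform whether non-drug treatment can help with dose reduction. One cautionary sentence and a few table columns would cost almost nothing, while a mis-sized trial is expensive. Whatever the cited source says about pilot size, it cannot turn a one-group change into a between-group effect.

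Much of this stands. The rationale is thin, the interval is wide, and a paired change should not on its own be taken as the effect for a controlled trial. But that caution is directed at whoever designs the later trial. It would not alter who is enrolled here, what is measured, which test is run or what estimate results. The passage on societal benefit states a hope and claims no result. Mean change with its interval, the two SDs, the pre-post correlation, the number of pairs and the divisor of the effect size are worth reporting. They come from data already planned, and most are by-products of the planned analyses. The text in question is also a brief lay summary on an ethics application, which is told to avoid technical terms, so their absence there is weak evidence of a faulty analysis.

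**Conclusion.** The observation is accurate, but it does not call for a change. N=30 is not shown to be wrong. The paired analysis validly estimates within-group change, and the Design text claims only preliminary effects from a pilot. The imprecision is real: for an assumed observed effect of 0.5, the interval is 0.12 to 0.88 with 30 pairs, and it moves little across 27 to 33. It is an ordinary price for a pilot of this size, and any report that gives the interval will show it.

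The serious figures, 56% down to 29% power in a later trial, rest on three assumptions outside the plan: a later team uses the paired value as a between-group effect, the observed value is 0.5, and a control arm would show 25% to 50% of the change. The plan states none of these. What is left is reporting detail that an analyst would sensibly fill in. Replacing the rationale with an exact-binomial one would be no gain, because the plan's feasibility and acceptability measures are not clearly counts out of 30.
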